## **LIST OF ABBREVIATIONS**

AE: Adverse event

AR: Adverse reaction

AUH: Aarhus University Hospital

ED: Emergency Department

eCRF: Electronic case report form

GCP: Good Clinical Practice

IV: Intravenous

LDK: Low-dose-ketamine

NRS: Numeric Rating Scale

RCT: Randomized Controlled Trial

SAE: Serious adverse event

SAR: Serious adverse reaction

SPIRIT: Standard Protocol Items: Recommendations for Interventional Trials

[figure not shown]
SUSAR: Suspected unexpected serious adverse reaction

## Overview

Registry and trial number	EudraCT number: 2021-005116-64
Date of registration	EudraCT: 16/09-2021
Sources of monetary or	
material support	Health Research Foundation of Central Denmark Region
Sponsor	[name], Aarhus University Hospital
Contact	[contact]
Primary investigator	[name], Aarhus University Hospital
Contact	[contact]
Title	Low-dose-ketamine for acute pain in the ED, a randomized,
	controlled, double-blinded, trial
Country of recruitment	Denmark
Condition studied	Acute pain in the ED
Intervention	LDK 0.1 mg/kg as an adjunct to morphine
Comparator	Morphine and placebo
Inclusion criteria	1) Emergency Department admission
	2) Age ≥ 18 years
	3) NRS ≥ 5
	4) Stable vital signs defined as systolic blood pressure ≥ 90
	mmHg, heart rate between 50 and 160 per minute, respiratory
	rate between 8 and 30 per minute, oxygen saturation greater
	than or equal to 92%
Exclusion criteria	1) Initial management by trauma-team
	2) Systolic blood pressure ≥ 180mmHg, severe untreated
	arrhythmia, unstable angina, recent myocardial infarction (< 30

	3) Symptoms of untreated hypert	hyroidism					
	4) Cirrhosis with ascites						
	5) Known/suspected pregnancy or breastfeeding						
	6) Patients for whom consent is n	ot obtainable or psychiatric					
	forced treatment.						
	7) Previously enrolled in the trial						
	8) Psychiatric illness prior to adm	ission defined as prior					
	psychosis/schizophrenia						
	9) Untreated diagnosed glaucoma						
	10) Known hypersensitivity to ket	amine or to any excipient or					
	prior use of ketamine with a nega	itive experience (i.e.					
	hallucinations)						
	11) Patient clearly influenced by c	lrugs or alcohol					
Study type	Interventional	Allocation Randomized (1:1)					
	Intervention model: Parallel	Masking: Double blinded					
	group						
Date of first screening	15-05-2022						
Target sample size	160						
Recruitment status	Recruiting						
Primary outcomes	The primary outcome measurement	ent is pain reduction after 10					
	min assessed on NRS.						

## **Trial flowchart**

\*15% of DDO AND a minimum of 0.05-0.1 mg/kg

## **Conflicts of interest**

The members of the project group have no conflicts of interest related to the current trial. A list of all conflict of interests is provided in Appendix 1. Trial site

## **Amendments**

Version 3.2

Version 3.1 (Apr. 19, 2023) to 3.2 (May 26, 2023)

• Clarifications in the screening process p 35

Version 3.0 (Apr. 19, 2022) to 3.1 Apr. 19, 2023)

• Corrections of minor typos and grammatical issues as well as minor clarifications and updated flowchart

- Precision on timepoint for registration of vital parameters (p 24)
- Precision of doses for patients with a daily use of opioids (last version 10% of daily dose, this version 15% of daily dose, AND a minimum of 0.05-0.1
- Precision of opioid doses for patients without a daily use of opioids (last version 0.1 mg/kg, this version 0.05-0.1 mg/kg)
- Stable pulse changed from 60-150 to 50-160
- Respiratory frequency changed from 8-24 to 8-30

## Version 2.0 (Nov. 22, 2021) to 3.0 (Apr. 19, 2022)

- Corrections of minor typos and grammatical issues as well as minor clarifications
- Addition of EudraCT
- Addition of Study Kits
- Addition on blinding details
- Addition of Hospital Pharmacy
- Clarification that that the unblinded pharmacy staff and nurse will not be involved in outcome evaluation, section 2.4
- Change in timepoints (not primary outcome time point)

## Version 1.0 (Oct. 4, 2021) to 2.0 (Nov. 22, 2021)

- IDMC is deleted from the protocol
- Criteria for patient withdrawel is described
- Exlusion criteria add
- Corrections in section 4.3.1, Safety and Harm, general considerations
- Corrections conserving Sponsors evaluation of SAR/SUSAR
- Labels added

## **BACKGROUND**

## 1.1 Pain in the ED – the participant population

## 1.1.1 Incidence and mortality

The Danish ED's have 1.8 million contacts each year and several studies find that 70-80% of these arrives from patients in pain.

This makes pain management an essential component of emergency medicine, but also a challenge in many cases and ineffective and/or delayed analgesia for patients attending the ED is a common feature 11,12,13.

Many variables contribute to this finding, including limited resources, lack of diligence for assessing and treating pain, side effect barriers, inadequate education of providers, and misconceptions on behalf of both patients and staff .

This is very unfortunate since the insufficient treatment of acute pain can lead to a number of complications, extended hospital stays, chronic pain, and prolonged course of illness.

A frequent and increasing challenge in the ED is the opioid-tolerant patients requiring acute pain management. They are a group of patients who seek medical help much more often than their opioid naïve counterparts, i.e. in the EDs. Since Denmark has one of the highest rates of opioid consumption in the world with 3-5% of the population using opioids daily or regularly , these patients have a strong presence in the ED.

Besides the above mentioned risks of complications, these patients are in risk of withdrawal symptoms and stigmatization because of the need for much larger doses of opioids to achieve pain relief than others. The staff in the ED can be reluctant to deviate from standard treatment and the patient can be perceived as pleading for opioids. These barriers may be the reason that opioid-tolerant patients often do not receive the doses of opioids required to relief their pain.

## 1.1.2 Treatment of pain

The primary basis for acute pain relief is the administration of systemic analgesic agents such as paracetamol (1 g x 4/24h), nonsteroidal anti-inflammatory drugs (NSAIDs) (400 mg x 3/24h) (if no contraindications), and opioids i.e. morphine 0.05- 0.1 mg/kg or fentanyl 0.5-1  $\mu$ g/kg.

Single opioid doses less than 0.1 mg/kg of intravenous morphine or 1  $\mu$ g/kg of intravenous fentanyl are likely to be inadequate for severe, acute pain and the need for additional doses should be anticipated.

#### 1.2 Low-dose ketamine – the trial intervention

## 1.2.1 The NMDA receptor

Ketamine functions primarily as an antagonist of the N-methyl-D-aspartate receptor (NMDA), thus counteracting signals and impulses, which lead to hyperalgesia, central sensitization and opioid tolerance, besides reducing the wind-up phenomenon, and activating descending inhibitory monoaminergic pain pathways via interaction with opioid receptors  .

#### 1.2.2 Use in pain treatment

Low-dose ketamine (LDK) has been used for decades and has been shown to be safe and effective in the reduction of acute postoperative pain and to reduce analgesic consumption in a variety of surgical interventions. Furthermore, LDK has been shown to prevent hyperalgesia and acute opioid tolerance due to the use of morphine and/or fentanyl.

LDK has been studied as analgesic in a variety of contexts, including as a stand-alone treatment, as an adjunct to opioids, and, to a lesser extent, as an intranasal formulation .

#### 1.2.3 Use in the ED

Regarding management of acute pain in the ED, finding alternatives to opioids has become increasingly interesting and LDK is studied both as a single agent  and as an adjunct to morphine . These studies overall found that both LDK and LDK + morphine had analgesic effects within the 60 minutes of administration, was opioid sparing, and had comparable safety profiles with placebo.

These studies conducted in the ED did not mention/or excluded patients with chronic pain and patients with prior opioid consumption. Therefore, these above mentioned RCTs provide no information regarding the management of patients with chronic pain and/or opioid tolerance.

Studies evaluating the benefits of LDK in the opioid tolerant patients have exclusively been conducted in the peri- and postoperative setting, and have been found to reduce postoperative pain and opioid requirements. Other (smaller) studies in the opioid tolerant population have found less or no benefit. Taken together, these studies suggest at least a mild benefit for ketamine in the opioid-tolerant population in the postoperative period.

We believe that patients with chronic pain and/or opioid tolerance would in particular benefit from LDK  when presenting in the ED with acute pain. As a NMDA receptor antagonist it presents analgesic effects independent of opioid tolerance.

To our knowledge, there are no prospective randomized trials that evaluate the role of LDK in managing a variety of acute, painful conditions in the opioid tolerant patients in the ED. Furthermore, additional data describing its safety and efficacy in the general ED setting is warranted.

#### 1.2.4 Ketamine

Ketamine's analgesic properties in sub-anesthetic doses (0.1-0.5 mg/kg) have been recognized for decades (average anesthetic induction dose is 2 mg/kg) and S-ketamine produces analgesia at plasma concentrations of 100 to 200 ng/mL, which represent a very small fraction of plasma concentrations after general anesthesia doses (9000–25,000 ng/mL).

The recommended sub-anesthetic dose of ketamine used in pain treatment or in the prehospital emergency setting is 0.125-0.25 mg/kg bolus given IV over at least one minute. In these doses LDK show analgesic effects without sedative or hypnotic effect. When used as per- and postoperative pain treatment at AUH doses are (perioperative) 0.3 mg/kg/h and (postoperatively) 0,02 mg/kg/h.

Studies from the ED  $^{46,59,60,61,62}$  finds little to no psychoperceptual effects at the dose of 0.1 mg/kg as will be used in this study.

## 1.2.5 Side effects reported following anesthetic doses

The side effects reported below are all related to doses and administration pace. They are reported after ketamine is used in anesthetic doses, and thus much larger doses than in this study.

## Frequency:

Very common: >10 %

Common: >1 % and <10 %

Not common: >0.1 % and <1 %

Rare: >0.01 % and <0.1 %

Very rare: <0.01 %

Not known (can't be estimated from available data)

Immune system disorders	
Rare	Anaphylaxis.
Neuropsychological manifestations	
Common	Emergence reactions (post-operative delirium)  vivid dream, nightmares, dizziness and restlessness, hallucnations  .
Frequency unknown	Dysphoria, anxiety, disorientation
Nervous system	
Not common	Enhanced muscle tone and spasms (resembling a partial motor or generalized motor seizure).
Eyes	
Common	Blurred vision
Not common	Diplopia, increased intraocular pressure, nystagmus
Heart	
Common	Transient tachycardia, elevated blood pressure and heart frequency
Rare	Arrhythmia, bradycardia
Vascular system	
Rare	Hypotension (when used in circulatory collapse)
Airways, thorax and mediastinum	
Common	Increased vascular resistance in the lung
	circulation, increased mucus secretion, increased

	need of oxygen, laryngospasm, transient respiratory depression*
Abdominal	. , .
Common	Nausea, vomiting, hypersalivation
Hepatobiliary dysfunction	
Frequency unknown	Abnormal test of liver function
	Drug induced liver injury**
Skin and subcutaneous tissue disorders	
Not common	Transient erythema and/or morbilliform rash,
	reactions at the injection site (pain and
	reddening)

- 1. When S-ketamine is used as single agent for anesthesia, up to 30 % of the patients are observed to have side effect in the recovery phase.
- 2. Frequency of these side effects can be reduced significantly by using a benzodiazepine.
- \*Large doses and rapid rate of administration

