## 2.1.2 Hypotheses

- The combination of IV LDK and IV morphine will be superior to IV morphine alone as regards analgesic effect measured as reduction on the NRS scale.
- The combination of IV LDK and IV morphine will provide a larger reduction on the NRS scale for patients with a prior use of opioids than for patients with no prior use of opioids.
- The combination of IV LDK and IV morphine will reduce the opioid consumption within the first hour.
- The frequency of side effects will be similar in the two treatment groups (ketamine vs. placebo)

\*\* After longer use (> 3 days).

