## 2.5 TRIAL PROCEDURES

## 2.5.1 Patients

The trial procedures will be limited to the interventions given with the first dose of morphine (see section 2.3)

Data will be obtained from the study specific eCRF and from the electronic medical records.

 $T_0$  defined as when the ED physician/nurse evaluates NRS and the PI gives the study medication.

The trial and observation period is  $T_0$  - 120 min.

	T 0	10 min	20 min	30 min	45 min	60 min	120 min
NRS	Х	х	Х	Х	Х	Х	х

Patient rated		Х					Х
pain relief*							
Vital	Χ	Х	Х	Χ	Х	Χ	Х
parameters							
Patient		х		Х			х
reported side							
effects**							
Physician							х
reported side							
effects***							
Provider							x
satisfaction							
score****							
Patient							x
satisfaction							
score							
RASS****	 	Х	Х	Х	Х	Х	Х

\*Patients will be asked to rate their pain relief on a 6-point scale ("worse pain," "no," "little," "moderate," "good," or "complete pain relief").

In addition, patients are encouraged to spontaneously report any other side effects/adverse advent. The timing of onset and resolution of all adverse effects during the observation period will be recorded.

- \*\*\*Physician-reported side effects: nystagmus, hypertension, respiratory depression, bradycardia, hallucinations.
- \*\*\*\*Provider satisfaction with pain control will be recorded on the 4-point Likert scale with 0 being "completely unsatisfied" and 3 being "very satisfied.
- \*\*\*\*\*Richmond Agitation-Sedation Scale (RASS) will be used to evaluate agitation or sedation. (appendix 2)

TRIAGE and TOKS (tidlig opsporing af kritisk sygdom) according to the standard at AUH will be used to evaluate differences in vital parameters.

\*\*Patient-Reported Side effects: nausea, lightheadedness or dizziness, disorientation, euphoria, itching, tinnitus, double vision, abnormal dreaming or hallucinations.

There will be no questionnaires for the participants to answer, they will be asked verbally and their answers will be entered in RedCap.

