**RASS** 

Need for rescue morphine and total use of morphine

Physician reported side effects: nystagmus, hypertension, respiratory depression, bradycardia, arrhythmia.

TOKS and triage values as standard procedures

Patient-reported side effects: nausea, lightheadedness or dizziness, dry mouth, disorientation, euphoria, itching, tinnitus, double vision, abnormal dreaming or hallucinations.

Patient satisfaction. To be able to compare with other and future studies "no pain" and "worst pain imaginable" are chosen as anchors.

Provider satisfaction with pain control will be recorded on the 4-point Likert scale with 0 being "completely unsatisfied" and 3 being "very satisfied.

Protocol violation.

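### Five effects that the protocol's own table lists for ketamine are on no prompted side-effect list, so the data cannot support similarity of the arms on those effects (minor)

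*Combined protocol and SAP*

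**What the plan says.** Protocol section 2.1.2 states as a hypothesis: "The frequency of side effects will be similar in the two treatment groups (ketamine vs. placebo". No margin is attached. Safety is part of the objective (2.1.5), and side effects are a secondary outcome (4.2.1).

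The only list of expected ketamine effects is the table in section 1.2.5. It ranks "Blurred vision" and "Nausea, vomiting, hypersalivation" as common (above 1% and below 10%), and gives "Dysphoria, anxiety, disorientation" with unknown frequency. Of the table's effects the section says "They are reported after ketamine is used in" anaesthetic doses, which it describes as far above the trial dose. Section 1.2.4 adds that research in emergency departments "finds little to no psychoperceptual effects at the dose of 0.1 mg/kg as will be used in this study".

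Section 2.5.1 has patients asked at 10, 30 and 120 minutes about "nausea, lightheadedness or dizziness, disorientation, euphoria, itching, tinnitus, double vision, abnormal dreaming or hallucinations". Section 6.2.2 gives the list as "nausea, lightheadedness or dizziness, dry mouth, disorientation, euphoria, itching, tinnitus, double vision, abnormal dreaming or hallucinations".

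Other routes exist. Section 2.5.1 encourages patients to volunteer any other effect and records the timing of all adverse effects during observation. Section 4.3.1 has the clinical team and investigator document suspected reactions. Level +1 of the Richmond scale (RASS, Appendix 2) covers anxious or apprehensive patients and is scored at every post-dose reading. The SAP compares the proportion with any adverse event during observation by a chi-square test.

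**The concern.** Symptoms that patients must volunteer are usually recorded less often than symptoms they are asked about. Five effects that the protocol itself attributes to ketamine are in the first group.

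The table does not explain the selection. Diplopia, ranked not common, is asked about; blurred vision, ranked common, is not. Nausea is asked about, but vomiting and hypersalivation from the same row are not. Euphoria, which is not in the table, is asked about, and dysphoria is not. Section 6.2.2 asks about dry mouth but not hypersalivation.

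When the hoped-for result is no difference and no margin is set, incomplete ascertainment can help the hypothesis. At stake is whether a statement of similar side effects may be read as covering effects that were never asked about.

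**Working it through.** **Comparison of the lists**

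| Effect | Rank in 1.2.5 | Asked in 2.5.1 | Asked in 6.2.2 | Physician lists |
|---|---|---|---|---|
| Blurred vision | Common | No | No | No |
| Vomiting | Common | No | No | No |
| Hypersalivation | Common | No | No | No |
| Dysphoria | Unknown | No | No | No |
| Anxiety | Unknown | No | No | No |

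The two sections also disagree with each other. Section 6.2.2 adds dry mouth for patients and, for physicians, replaces hallucinations with arrhythmia.

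**Inputs.** From the documents: 1:1 allocation, n = 116 in the SAP (58 per arm if split equally), two-sided 5% level, chi-square test. The documents state no side-effect rate, margin or power, so there is no plan figure to reproduce. Every rate and capture share below is an assumption.

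**One effect.** If a share s of cases is captured in both blinded arms, the observed difference is s × (true difference). It shrinks towards zero whenever the effect is commoner on LDK. Power below is by exact enumeration of two binomials, uncorrected chi-square, 58 per arm:

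| True risk, LDK vs control | s = 1 | s = 0.5 | s = 0.25 |
|---|---|---|---|
| 20% vs 5% | 72% | 38% | 17% |
| 10% vs 5% | 17% | 9% | 3% |
| 10% vs 2% | 45% | 19% | 4% |
| 5% vs 1% | 19% | 4% | under 1% |

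The first row lies above the table's ceiling for a common effect, which is below 10% even at anaesthetic doses. In the other rows power is below 50% even with full prompting.

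**The SAP's composite, any adverse event.** Let p be the risk of any prompted effect and q the risk of any of the five, taken as independent. Observed risk = 1 − (1 − p)(1 − q·s). With p = 40% (LDK) vs 30% (control) and q = 10% vs 5%:

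- s = 1: (1 − 0.60 × 0.90) − (1 − 0.70 × 0.95) = 46.0% − 33.5% = 12.5 points, power 27%
- s = 0.5: 43.0% − 31.75% = 11.25 points, power 23%
- s = 0.25: 41.5% − 30.875% = 10.6 points, power 22%

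The loss is 12.5 − 11.25 = 1.25 points, or 12.5 − 10.625 = 1.9 points.

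Same p, other values of q:

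| q, LDK vs control | s = 1 | s = 0.5 | s = 0.25 |
|---|---|---|---|
| 5% vs 2% | 11.6 | 10.8 | 10.4 |
| 20% vs 5% | 18.5 | 14.25 | 12.1 |
| 10% vs 10% | 9.0 | 9.5 | 9.75 |

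(Differences in percentage points.) The loss is about 1 point in the first row and 4 to 6 in the second. In the third row omission enlarges the observed difference by up to 1 point.

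**Precision.** At an assumed 30% in both arms, the 95% interval half-width is 1.96 × √(2 × 0.3 × 0.7 / 58) = 0.167, about 17 points; with 80 per arm it is about 14. The shift in the modest scenarios is small beside that.

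**The case against.** The strongest reply is that the checklist is only one of several routes. Patients are invited to volunteer anything else, all adverse effects in the observation period are to be timed, clinicians document suspected reactions, vomiting is visible to staff, and RASS +1 reaches anxiety. Both arms get the same questions under blinding. A patient who vomits and reports nausea already counts in the composite, and positive correlation between symptoms would generally make the loss smaller than the independence figures. The table describes anaesthetic doses, and little psychoperceptual effect is expected at the trial dose.

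Most of this stands, and it limits the size of the point. Some of the routes are weaker than they look:

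- Timing recorded effects adds no question.
- Section 4.3.1 excludes events that are natural consequences of the reason for admission, so vomiting in a patient with abdominal pain could be lost.
- The SAP names the Ramsay scale while the protocol collects RASS, so RASS +1 may not reach the analysis.
- No route prompts for dysphoria, blurred vision or hypersalivation, which patients would largely have to volunteer.

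A reader might infer that harms on LDK are under-counted and that the comparison is biased towards similarity. The documents do not show this. They give no arm-specific rate for any of the five effects, and the composite moves slightly the other way if the five are equally common. Nor do they show a list slanted towards pleasant effects: disorientation, nausea, dizziness, and abnormal dreaming or hallucinations are all asked about.

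**Conclusion.** The omission is a matter of record: five effects in the protocol's own table are on no prompted list, three of them ranked common. It follows that the data will be weaker for these effects than for the prompted ones, and that incomplete capture would shrink any true excess on LDK for a single effect. Bias towards similarity is therefore plausible but not demonstrated.

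The size is unknown. With modest assumed rates it is about 1 to 2 points on the composite. It reaches 4 to 6 points only if the five together affect 20% vs 5%, which nothing in the documents supports at 0.1 mg/kg. A fall from 15 points to 4 to 8, which a reader might compute from 20% vs 5% on one effect (15 × 0.25 = 3.75; 15 × 0.5 = 7.5), rests on a rate above the table's ceiling for common effects and on a different endpoint from the SAP's. Severity is minor.

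**What to change.** For patients still to be observed: use one identical patient list in sections 2.5.1 and 6.2.2, with blurred vision, vomiting, hypersalivation and dysphoria/anxiety added as yes/no items at the existing 10, 30 and 120 minute readings. Align the two physician lists at the same time.

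For patients already observed: report prompted and volunteered effects separately by arm, with counts for each individual effect, and do not claim similarity for effects that were never asked about. State in the SAP how volunteered effects and RASS +1 enter the any-adverse-event endpoint, and reconcile Ramsay with RASS. Since the SAP already refers to 116 included patients, this reporting part may be all that can still be used.

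Cost: about four short verbal items per reading and one extra split in the side-effect table. Prompting will also bring in background symptoms in both arms, which can slightly dilute the composite difference, so the individual effects should be shown beside it.
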